** NOT FOR USE – EXAMPLE ONLY**

This Questionnaire is protected by copyright. To obtain a License to use this Questionnaire, contact the McMaster Industry Liaison Office, McMaster University, email: [contact]

For Review Purposes Only

25. How much of the time during the last 2 weeks have you felt tearful or upset? Please choose an option from

- 1 ALL OF THE TIME
- 2 MOST OF THE TIME
- 3 A GOOD BIT OF THE TIME
- 4 SOME OF THE TIME
- 5 A LITTLE OF THE TIME
- 6 HARDLY ANY OF THE TIME
- 7 NONE OF THE TIME

26. How much of the time during the last 2 weeks have you been troubled by accidental soiling of your underpants? Please choose an option from

- 1 ALL OF THE TIME
- 2 MOST OF THE TIME
- 3 A GOOD BIT OF THE TIME
- 4 SOME OF THE TIME
- 5 A LITTLE OF THE TIME
- 6 HARDLY ANY OF THE TIME
- 7 NONE OF THE TIME

27. How much of the time during the last 2 weeks have you felt angry as a result of your bowel problem? Please choose an option from

- 1 ALL OF THE TIME
- 2 MOST OF THE TIME
- 3 A GOOD BIT OF THE TIME
- 4 SOME OF THE TIME
- 5 A LITTLE OF THE TIME
- 6 HARDLY ANY OF THE TIME
- 7 NONE OF THE TIME

Copyright © 1988 McMaster University, Hamilton, Ontario, Canada

The Inflammatory Bowel Disease Questionnaire (IBDQ), authored by [name] et al, is the copyright of McMaster University (Copyright ©1988, McMaster University). The IBDQ has been provided under license from McMaster University and must not be copied, distributed or used in any way without the prior written consent of McMaster University.
Contact the McMaster Industry Liaison Office at McMaster University, email: [contact] for licensing details

** NOT FOR USE – EXAMPLE ONLY**

This Questionnaire is protected by copyright. To obtain a License to use this Questionnaire, contact the McMaster Industry Liaison Office, McMaster University, email: [contact]

For Review Purposes Only

28. To what extent has your bowel problem limited sexual activity during the last 2 weeks? Please choose an option from

- 1 NO SEX AS A RESULT OF BOWEL DISEASE
- 2 MAJOR LIMITATION AS A RESULT OF BOWEL DISEASE
- 3 MODERATE LIMITATION AS A RESULT OF BOWEL DISEASE
- 4 SOME LIMITATION AS A RESULT OF BOWEL DISEASE
- 5 A LITTLE LIMITATION AS A RESULT OF BOWEL DISEASE
- 6 HARDLY ANY LIMITATION AS A RESULT OF BOWEL DISEASE
- 7 NO LIMITATION AS A RESULT OF BOWEL DISEASE

29. How much of the time during the last 2 weeks have you been troubled by nausea or feeling sick to your stomach? Please choose an option. from

- 1 ALL OF THE TIME
- 2 MOST OF THE TIME
- 3 A GOOD BIT OF THE TIME
- 4 SOME OF THE TIME
- 5 A LITTLE OF THE TIME
- 6 HARDLY ANY OF THE TIME
- 7 NONE OF THE TIME

30. How much of the time during the last 2 weeks have you felt irritable? Please choose an option from

- 1 ALL OF THE TIME
- 2 MOST OF THE TIME
- 3 A GOOD BIT OF THE TIME
- 4 SOME OF THE TIME
- 5 A LITTLE OF THE TIME
- 6 HARDLY ANY OF THE TIME
- 7 NONE OF THE TIME

Copyright © 1988 McMaster University, Hamilton, Ontario, Canada

The Inflammatory Bowel Disease Questionnaire (IBDQ), authored by [name] et al, is the copyright of McMaster University (Copyright ©1988, McMaster University). The IBDQ has been provided under license from McMaster University and must not be copied, distributed or used in any way without the prior written consent of McMaster University.
Contact the McMaster Industry Liaison Office at McMaster University, email: [contact] for licensing details

** NOT FOR USE – EXAMPLE ONLY**

This Questionnaire is protected by copyright. To obtain a License to use this Questionnaire, contact the McMaster Industry Liaison Office, McMaster University, email: [contact]

For Review Purposes Only

31. How often during the past 2 weeks have you felt a lack of understanding from others?
Please choose an option from

- 1 ALL OF THE TIME
- 2 MOST OF THE TIME
- 3 A GOOD BIT OF THE TIME
- 4 SOME OF THE TIME
- 5 A LITTLE OF THE TIME
- 6 HARDLY ANY OF THE TIME
- 7 NONE OF THE TIME

32. How satisfied, happy, or pleased have you been with your personal life during the past 2 weeks? Please choose one of the following options from

- 1 VERY DISSATISFIED, UNHAPPY MOST OF THE TIME
- 2 GENERALLY DISSATISFIED, UNHAPPY
- 3 SOMEWHAT DISSATISFIED, UNHAPPY
- 4 GENERALLY SATISFIED, PLEASED
- 5 SATISFIED MOST OF THE TIME, HAPPY
- 6 VERY SATISFIED MOST OF THE TIME, HAPPY
- 7 EXTREMELY SATISFIED, COULD NOT HAVE BEEN MORE HAPPY OR PLEASED

Copyright © 1989 McMaster University, Hamilton, Ontario, Canada

The Inflammatory Bowel Disease Questionnaire (IBDQ), authored by [name] et al, is the copyright of McMaster University (Copyright ©1989, McMaster University). The IBDQ has been provided under license from McMaster University and must not be copied, distributed or used in any way without the prior written consent of McMaster University.
Contact the McMaster Industry Liaison Office at McMaster University, email: [contact] for licensing details

** NOT FOR USE - EXAMPLE ONLY**

This Questionnaire is protected by copyright. To obtain a License to use this Questionnaire, contact the McMaster Industry Liaison Office, McMaster University, email: [contact]

Appendix 2 Subject Diary Script

Subject Diary Script

Subject Daily Diary Questions

1. Did you take your study medication today?
 - a) Yes NoIf Yes;
 - b) Did you take the study medication at least 1 hour before or at least 2 hours after a meal? Yes No
2. Evaluate today's bowel movement frequency.
 - a) Number of bowel movement today _____
3. Have you noticed any blood in your bowel movement?
 - a) Normal = (*No blood*)
 - b) Streaks of blood
 - c) Obvious blood
 - d) Mostly blood

Note: That a bowel movement may consist of one or multiple stools; what one experiences in one visit to the toilet is classified as a bowel movement. For the rectal bleeding score, the worst score during the day is the one which will be recorded.

Bowel Movement (BM) Frequency (daily)

To determine the effect of medical therapy on your bowel movement frequency, we need you to define your "usual" non-ill state of health.

- What is your normal bowel movement frequency?

Each day during the trial you will assess your bowel movement frequency. This will be entered into your daily diary.

- What is your bowel movement frequency today?

Rectal Bleeding Occurrence (daily)

Each day during the trial you will assess your rectal bleeding. This assessment should be based on your worst episode of bleeding that day. One of the four (4) choices below will be entered into your daily diary:

Have you noticed any blood in your bowel movement? For example:

- If you see NO blood on the bowel movement or in the toilet water or visible anywhere in the toilet, enter a bleeding score of 0.

- If you see only red streaks of blood on the surface of the bowel movement, enter a bleeding score of 1.
- If you see red streaks of blood on the surface of the bowel movement and/or in the toilet water and/or visible anywhere in the toilet, enter a bleeding score of 2.
- If your bowel movement is mostly or totally blood, enter a bleeding score of 3.

Statistical Analysis Plan

Title of trial:

A randomized, double-blind, placebo-controlled, multicenter study investigating the efficacy and safety of mesalamine 2 g extended release granules (sachet) for maintenance of clinical and endoscopic remission in ulcerative colitis

NCT number:

NCT02522780

Sponsor trial code:

000175

Date:

02 Apr 2018

STATISTICAL ANALYSIS PLAN

A Randomized, Double-Blind, Placebo-Controlled, Multicenter Study Investigating the Efficacy and Safety of Mesalamine 2 g Extended Release Granules (Sachet) for Maintenance of Clinical and Endoscopic Remission in Ulcerative Colitis

000175

Investigational Product: Mesalamine 2 g Extended Release Granules (Sachet)

Indication: Maintenance of clinical and endoscopic remission in ulcerative colitis

Phase: 3

Author: 

Date of issue: 02-Apr-2018

Version: 3.0

The information in this document is confidential and is proprietary to Ferring Pharmaceuticals A/S or another company within the Ferring Group. It is understood that information in this document shall not be disclosed to any third party, in any form, without prior written consent of an authorised officer of Ferring Pharmaceuticals A/S or another company within the Ferring Group

Change log

Version No.	Effective Date	Reason for the Change / Revision	Supersedes
2.0	August 7, 2015	
 - Reflected protocol amendments 1 and 2 - Addressed FDA's comments on the initial SAP and modified related places accordingly 
 o Changed to exclude subjects who are rolled over from the placebo group in the 000174 trial via Pathway 1 from the primary analysis, and consequently, the sample size was increased to approximately 260 subjects o Definition of the ITT analysis set was changed to exclude above subjects o Added all randomized and modified ITT analysis sets to the sensitivity analysis o Strata in each analysis set were defined accordingly o Added sensitivity analyses using multiple imputation methods and pattern mixture models under missing at random and missing not at random assumptions, respectively. 	Version 1.0

1.1 Definitions/ Abbreviations

1.1.1 Definition of Terms

Terms	Definitions
Clinical Response Score	Stool frequency and rectal bleeding subscale of Clinical and Endoscopic Response Score
Endoscopic Response Score	Flexible sigmoidoscopy findings subscale of Clinical and Endoscopic Response Score

1.1.2 Abbreviations

Abbreviations	Meaning of abbreviations in document
ADR	Adverse drug reaction
AE	Adverse event
ALT	Alanine aminotransferase
ANCOVA	Analysis of covariance
AST	Aspartate aminotransferase
ATC	Anatomical therapeutic chemical
CRP	C-reactive protein
ECG	Electrocardiogram
eGFR	Estimated glomerular filtration rate
GEE	Generalized estimating equations
GGT	Gamma glutamyl transferase
HBV	Hepatitis B virus
HCV	Hepatitis C virus
HIV	Human immunodeficiency virus
HRQoL	Health-related quality of life
IBDQ	Inflammatory bowel disease questionnaire
IMP	Investigational medicinal product
INR	International normalized ratio
ITT	Intention-to-treat
MAR	Missing at random
MedDRA	Medical dictionary for regulatory activities
MI	Multiple imputation
mITT	Modified ITT
MNAR	Missing not at random
PMM	Pattern mixture model
PP	Per protocol
PT	Preferred term
QD	Once daily
QTc	Corrected QT interval
SOC	System organ class

Abbreviations

TEAE

UC

US

WBC

WHO-Drug

Meaning of abbreviations in document

Treatment-emergent adverse event

Ulcerative colitis

United states

White blood cell

World health organization drug dictionary

2 Trial Objectives and Endpoints

2.1 Objectives

2.1.1 Primary objective

- To demonstrate the efficacy of mesalamine 2 g extended release granules (sachet) once daily (QD) compared to placebo in the maintenance of clinical and endoscopic remission of ulcerative colitis (UC)

2.1.2 Secondary objective

- To evaluate the efficacy of mesalamine 2 g extended release granules (sachet) utilizing the Clinical and Endoscopic Response Score, Clinical Response Score subset, and frequency of treatment failures
- To assess C-reactive protein (CRP) levels and fecal calprotectin levels
- To assess health-related quality of life (HRQoL) using the Inflammatory Bowel Disease Questionnaire (IBDQ)
- To assess the incidence and severity of adverse events (AEs) and abnormal laboratory values

2.2 Endpoints

2.2.1 Primary endpoint

The primary efficacy endpoint is the proportion of subjects in remission, defined by the Clinical and Endoscopic Response Score ([Table 1](#)) at Month 6 as a score of,

- 0 for rectal bleeding, and
- 0 or 1 for stool frequency, and
- 0 or 1 for endoscopic score.

The endoscopic score will be determined by an independent central reader.

Table 1 Clinical and Endoscopic Response Score (0 – 9)

Components	Subscale	Severity	Score
CLINICAL RESPONSE (Subject's Symptoms)	Stool Frequency^a (daily)	Normal number of stools for subject	0
		1 to 2 stools more than normal	1
		3 to 4 stools more than normal	2
		≥5 stools more than normal	3
	Rectal Bleeding^b (daily)	No blood seen	0
		Streaks of blood with stool	1
		Obvious blood with stool	2
		Blood alone passes	3
ENDOSCOPIC RESPONSE (Objective Evidence of Inflammation)	Flexible Sigmoidoscopy Findings	Normal or inactive disease	0
		Mild disease (erythema, decreased vascular pattern, granularity)	1
		Moderate disease (marked erythema, absent vascular pattern, any friability, erosions)	2
		Severe disease (spontaneous bleeding, ulceration)	3

Adapted from: Schroeder et al. (1987)(1); Sninsky et al. (1991)(2); Modified by Ferring Group, 2014

- a. Each subject serves as his or her own control to establish the degree of abnormality of the stool frequency.
 b. The daily bleeding score represents the most severe bleeding of the day.

2.2.2 Secondary endpoints

- The proportion of subjects in clinical remission at Months 2, 4, and 6, defined as a score of 0 for rectal bleeding and 0 or 1 for stool frequency based on Clinical Response Score subset of the Clinical and Endoscopic Response Score
- Time to relapse, defined as number of days from randomization to the day of withdrawal due to escalation of therapy (i.e., surgical therapy, use of steroids, immunosuppressive or immunomodulating drugs, biologics, increase dose of 5 aminosalicylic acid [5-ASA] in any form)
- The proportion of subjects with an increase from baseline in the Clinical and Endoscopic Response Score by 2 or more points in at least 1 component or by 1 or more points in at least 2 components at Month 6
- The change from baseline in serum CRP levels at Months 2, 4, and 6
- The change from baseline in fecal calprotectin levels at Months 2, 4, and 6
- The change from baseline to each scheduled assessment for published and validated domain scores of the IBDQ
- Safety assessed by incidence and severity of AEs and abnormal laboratory values

3 Trial design

This is a randomized, double-blind, placebo-controlled, parallel-group, multicenter, international, Phase 3 trial to investigate the safety and efficacy of mesalamine 2 g extended release granules (sachet) for maintenance of clinical and endoscopic remission in subjects with UC. Subjects who are in remission can be enrolled in the current trial via 1 of 3 pathways.

- Pathway 1: Subjects who are in remission following 8 weeks of double-blind treatment in Study 000174 can be randomized into Study 000175. The clinical and endoscopic remission criteria for Study 000174 include a Clinical and Endoscopic Response Score as a score of 0 for rectal bleeding and 0 or 1 with at least 1 point decrease from baseline for stool frequency, with an endoscopic score of 0 or 1.
- Pathway 2: Subjects in remission at the end of the 8-week open-label treatment period in Study 000174 will be allowed to be randomized into Study 000175.
- Pathway 3 – de novo: Subjects who did not participate in Study 000174 can also be enrolled; these subjects will have been treated with various medications for UC (excluding biologics and long-term [≥ 6 months] immunosuppressants) and will have been in remission for < 1 year. These de novo subjects will undergo a 72-hour mesalamine washout prior to entering the current trial and will have a Clinical and Endoscopic Response Score assessment to ensure eligibility.

All eligible subjects will be randomized during Visit 1/Day 0 (start of maintenance) to 1 of the following treatments:

- one mesalamine 2 g extended release granules (sachet) QD (2 g/day) OR
- one 2 g placebo sachet to match mesalamine extended release granules (sachet)

Dose will be administered QD at least 1 hour before or at least 2 hours after a meal at approximately the same time each day. The sachet will be emptied on the tongue and swallowed with at least 8 ounces (240 mL) of water. For all subjects, the first dose of investigational medicinal product (IMP) will be administered the day following randomization/Visit 1.

During the 6-month trial period, all subjects will visit the trial site 5 times for safety and efficacy evaluations: baseline, Week 2, and Months 2, 4, and 6. On a daily basis, subjects will record clinical symptoms (stool frequency and rectal bleeding) in an electronic diary. The Clinical and Endoscopic Response Score assessments will be performed at baseline and Month 6. After 6 months of treatment, subjects will be evaluated for remission, defined as a Clinical and Endoscopic Response Score of rectal bleeding score of 0 and stool frequency scores of 0 or 1, with an endoscopic score of 0 or 1. Whereas, subjects will only have a Clinical Response Score assessment at Months 2 and 4. De novo subjects will have a complete screening visit, and if they are judged to be in clinical and endoscopic remission based on their Clinical and Endoscopic Score at

baseline/randomization, they will continue with the 6 month assessment for safety and efficacy evaluations.

Flexible sigmoidoscopy/colonoscopy will be video recorded and transferred to the independent central reader. The details of the tools, recording, data transfer, and assessment will be documented in an Imaging Charter. If the local site's endoscopic reading determines the subject is ineligible, the subject will be screen failed (Pathway 3 – de novo). If the local site's endoscopic reading determines that the subject is eligible, the flexible sigmoidoscopy recording will be sent to the independent central reader for final determination of eligibility (Pathway 3 – de novo). For subjects rolling over from the 000174 trial (Pathway 1 and 2), 000175 eligibility will be derived from the final end of treatment (EOT) independent central read. A flexible sigmoidoscopy will also be performed at Month 6, which will also be sent to the independent central reader for endoscopic endpoint scoring for all subjects.

The schedule of trial procedures is presented in [Appendix 2](#).

3.1 General Design Considerations

This trial is designed as a randomized, double-blind, placebo-controlled trial with 6 months of treatment. Subjects will be randomized by pathway of enrollment, and Pathway 1 will be further stratified by the treatment group assigned in the 000174 trial.

The endoscopic score will be determined by an independent central reader.

3.2 Determination of Sample Size

The true remission rates at Month 6 for mesalamine 2 g extended release granules (sachet) and placebo regimens were assumed as 68% and 49%, respectively, based on The mesalamine Study Group (1996)(3), Hawkey et al (1997)(4), and Apriso™ package insert (2009)(5). Under these assumptions, a sample size of 120 randomized subjects per group will provide at least 85% power to detect a statistically significant treatment group difference in the remission rate at a two-sided 0.05 significance level using the chi-square test. To maintain the power for the primary efficacy analysis that excludes subjects who are rolled over from the placebo group in the 000174 trial via Pathway 1, approximately 260 subjects will be randomized.

4 Subject Disposition

The number of screened subjects will be summarized, and for subjects not randomized, the primary reason for exclusion from randomization will be summarized.

The number and percentage of subjects who are randomized, are treated with IMP, prematurely discontinued, and completed the trial will be summarized with the reason of premature discontinuations.

The time to discontinuation will be summarized by the Kaplan-Meier estimates, and the treatment group difference will be tested by the log-rank test. In addition, reason-specific discontinuation will be summarized by the cumulative incidence estimates.

5 Protocol Deviations

The following protocol deviations will be identified as major protocol deviations:

- Overall IMP compliance of less than 80%
- Not taking the randomized IMP
- Taking prohibited medications

The final definition of major protocol deviations will be determined prior to breaking the blind.

The number and percentage of subjects with protocol deviations will be summarized.

6 Analysis sets

For each analysis set, the number and percentage of subjects excluded from it will be summarized by the reason of the exclusion.

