4.2 Method of Assigning Subjects to Treatment Groups

At Visit 1/Baseline, subjects will be randomly assigned, in a 1:1 ratio, to 1 of 2 treatment groups based on a centralized computer-generated randomization schedule via an interactive response technology (IRT). The randomization will be stratified by the pathway of enrolment, and Pathway #1 will be further stratified by the treatment group assigned in the 000174 trial.

Re-enrollment of subjects is prohibited under any circumstances.

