9.2 Subject Disposition

The number of screened subjects will be summarized, and for subjects not randomized, the primary reason for exclusion from randomization will be summarized.

The number and percentage of subjects who are randomized, are treated with IMP, prematurely discontinued, and completed the trial will be summarized with the reasons for premature discontinuations.

The time to discontinuation will be summarized by the Kaplan-Meier estimates, and the treatment group difference will be tested by the log-rank test. In addition, reason-specific discontinuation will be summarized by the cumulative incidence estimates.

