9.1 General Considerations

All statistical tests will be conducted at a two-sided 0.05 significance level.

All secondary endpoints will be tested without adjustment for multiplicity.

Randomization strata will be included in stratified analyses for efficacy endpoints. For the ITT, mITT, and PP analysis sets, randomization strata will be defined as follows:

- Stratum 1: Pathway 1 (mesalamine 4 g extended release granules arm in the 000174 trial)
- Stratum 2: Pathway 2
- Stratum 3: Pathway 3

Randomization strata for the all randomized analysis set will be defined as follows:

- Stratum 1: Pathway 1a (placebo arm in the 000174 trial)
- Stratum 2: Pathway 1b (mesalamine 4 g extended release granules arm in the 000174 trial)
- Stratum 3: Pathway 2
- Stratum 4: Pathway 3

Stool frequency and rectal bleeding scores at each visit will be calculated as an average of the daily scores collected within 5 days prior to the visit (excluding the visit day and the day before the visit day if the bowel preparation is needed on the day before the visit). If the daily scores in this period are available for fewer than 3 days, the average score will be considered missing. The average scores will be rounded to the nearest integer for the final score determination (e.g., 0.3 will be rounded to 0, and 0.5 will be rounded to 1). Handling of missing data in the statistical analyses will be described for each endpoint.

For the endoscopic assessment, the outcomes determined by the independent central reading procedure will be used for all analyses.

For visit-based data, the data collected on the day that is closest to the scheduled trial day within a window will be assigned to the corresponding analysis visit. [Table 2](#) shows the scheduled trial day and window for each analysis visit.

Table 2 Scheduled trial day and window for analysis visits

Analysis visit	Scheduled trial day	Window
Baseline	Day 1	prior to the first dose of IMP

Analysis visit	Scheduled trial day	Window
Week 2	Day 14	Day 1 to Day 35
Month 2	Day 56	Day 36 to Day 84
Month 4	Day 112	Day 85 to Day 140
Month 6	Day 168	Day 141 or after

If the closest day cannot be uniquely identified for an analysis visit, the data collected on an earlier trial day will be assigned to the analysis visit.

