9.3 Secondary Endpoint(s)

The following key secondary endpoints will be analyzed for the ITT analysis set.

- The proportion of subjects in clinical remission at Months 2, 4, and 6, defined as a score of 0 for both rectal bleeding and stool frequency based on Clinical Response Score subset of the Clinical and Endoscopic Response Score
- Time to relapse, defined as number of days from randomization to the day of withdrawal due to escalation of therapy (i.e., surgical therapy, use of steroids, immunosuppressive or immunomodulating drugs, biologics, increase dose of 5 ASA in any form)

- The proportion of subjects with an increase from baseline in the Clinical and Endoscopic Response Score by 2 or more points in at least 1 component or by 1 or more points in at least 2 components at Month 6
- The change from baseline in serum CRP levels at Months 2, 4, and 6
- The change from baseline in fecal calprotectin levels at Months 2, 4, and 6

The proportion of subjects in clinical remission at Months 2, 4, and 6 will be analyzed by the generalized estimating equations (GEE) approach as longitudinal binary outcomes. The model will include the randomization strata, treatment, time, and treatment- by-time interaction. The clinical remission rates and odds ratio will be estimated for each time point. The overall treatment difference over 6 months will be estimated as the main effect for treatment in the model. The missing values will be imputed as non-remission, and an unstructured working correlation matrix will be used.

The time to relapse will be analyzed by the log-rank test stratified by the randomization strata. If a subject does not have the relapse by Day 168, the time to relapse will be censored at the earlier of the day that the last visit day or Day 168. The hazard ratio of relapse for mesalamine relative to placebo will be estimated (including the 95% CI) using the stratified Cox proportional hazards model with treatment group as a factor and the randomization strata as a stratification variable.

The proportion of subjects with an increase from baseline in the Clinical and Endoscopic Response Score by 2 or more points in at least 1 component or by 1 or more points in at least 2 components at Month 6 will be analyzed using the same statistical method used for the primary efficacy analysis.

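### The log-rank test of time to discontinuation names no stratification although randomization is stratified by pathway: valid, but slightly conservative if discontinuation risk differs between pathways

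*SAP*

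**What the plan says.** SAP section 4 (Subject Disposition) reads: "The time to discontinuation will be summarized by the Kaplan-Meier estimates, and the treatment group difference will be tested by the log-rank test". Protocol 9.2 matches it: "the treatment group difference will be tested by the log-rank test". Neither sentence mentions strata, and SAP section 4 names no analysis set for the test.

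On randomization, Protocol 4.2 states: "The randomization will be stratified by the pathway of enrolment". SAP 3.1 adds that "Pathway 1 will be further stratified by the treatment group assigned in the 000174 trial". That makes four randomization strata.

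For the other log-rank test in the plan, SAP 9.3 states: "The time to relapse will be analyzed by the log-rank test stratified by the randomization strata". The general rule in SAP 9.1 is: "Randomization strata will be included in stratified analyses for efficacy endpoints". SAP 9.1 then defines three strata for the ITT, mITT and PP sets and four for the all randomized set.

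**The concern.** A programmer who follows the text would run the discontinuation test unstratified. It is a disposition analysis, and the rule in SAP 9.1 covers efficacy endpoints.

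The strata enter the trial by different routes: remission after double-blind placebo or mesalamine in Study 000174, remission only after a further open-label course, or de novo entry from various prior medications after a washout. Different withdrawal risks are plausible. The sponsor already adjusts for these strata in the primary analysis and in the secondary models.

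When arms are balanced within strata by design but the strata are ignored in the analysis, the pooled variance includes between-stratum variation that the randomization has removed. The test then rejects too rarely under the null. Under an effect common to all strata, mixing strata of different risk also pulls the observed hazard ratio toward 1.

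What is at stake is a little power in one formal between-arm comparison. Its p-value is likely to be read beside the relapse p-value, since every relapse event is by definition a withdrawal.

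**Working it through.** **The plan's own figure.** The only power statement concerns the primary endpoint, where remission rates "were assumed as 68% and 49%, respectively". With pooled variance and no continuity correction:

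n = [1.960·√(2·0.585·0.415) + 1.036·√(0.68·0.32 + 0.49·0.51)]² / 0.19² = (1.366 + 0.709)² / 0.0361 ≈ 119.2, so 120 per group.

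Power at 120 per group is 85.2%. The stated figure is reproduced and this point does not affect it. The plan gives no power or event count for time to discontinuation.

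**Inputs from the documents.** About 260 subjects, 1:1 (Protocol 3.2); four strata (Protocol 4.2, SAP 9.1); follow-up to Day 168. SAP 9.1 sets the level: "All statistical tests will be conducted at a two-sided 0.05 significance level".

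**Assumptions (not in the documents).** Exponential times to discontinuation, censored at Day 168; hazard ratio 0.6 in every stratum; and the stratum sizes and placebo risks below. Strata are ordered Pathway 1 placebo / Pathway 1 mesalamine / Pathway 2 / Pathway 3.

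**Check on event count.** With a placebo risk of 35% in all strata, the mesalamine risk is 1 − 0.65^0.6 = 22.8%. Expected events are 130·0.35 + 130·0.228 ≈ 75. The Schoenfeld approximation gives power Φ(√(75/4)·|ln 0.6| − 1.960) = Φ(0.252) = 59.9%. The simulation for this case gives 60.0%.

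**Simulation, strata of 20/90/70/80, 10,000 runs per cell.**

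| Placebo discontinuation by stratum (%) | Power, unstratified | Power, stratified | Type I error, unstratified | Type I error, stratified |
|---|---|---|---|---|
| Equal: 35 in all | 60.0% | 59.9% | 5.0% | 5.2% |
| Mild: 25/30/40/40 | 59.6% | 59.8% | 5.1% | 5.3% |
| Moderate: 20/25/35/50 | 57.3% | 59.3% | 4.3% | 4.8% |
| Extreme: 10/15/35/65 | 51.1% | 60.3% | 2.6% | 4.8% |

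The simulation standard error is about √(0.6·0.4/10,000) = 0.5 points for power and √(0.05·0.95/10,000) = 0.2 points for type I error.

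**Other stratum splits, 6,000 runs per cell (power, unstratified vs stratified).**

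| Split | Equal | Moderate | Extreme |
|---|---|---|---|
| 10/30/40/180 | 60.0% vs 59.7% | 69.3% vs 70.3% | 73.9% vs 78.5% |
| 20/120/60/60 | 59.3% vs 59.3% | 54.4% vs 56.0% | 45.7% vs 55.0% |

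A further run with 10/40/20/60 per arm and placebo risks of 15/25/50/40% (4,000 simulations) gave 56.8% unstratified and 58.7% stratified.

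**Reading.** The gain is about 0 with equal or mild differences, about 1 to 2 points with moderate ones, and 4.6 to 9.3 points with extreme ones. The largest loss from stratifying is about 0.35 points (60.03% vs 59.68%), which is within simulation error.

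**The case against.** The strongest reply is that this is a preference about a disposition summary. Time to discontinuation is not a listed endpoint, has no power target and feeds no decision. The SAP follows the protocol on this point, and SAP 9.1 ties the strata to efficacy endpoints. An unstratified log-rank test also sits naturally beside pooled Kaplan-Meier curves. All of this stands, and it is why the point ranks low. It does not remove the small gain from analysing a formal comparison by the groups used to randomize.

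Four stronger readings are tempting, and the documents do not support them:

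- **The test is invalid.** It is not. Its simulated type I error stays at about 5% or falls below it.
- **Power is certainly lost.** The loss depends on pathway differences that the documents do not quantify. With equal risk there is none.
- **The test is in effect an efficacy result.** Discontinuation is all-cause. Protocol 4.4 also lists adverse events, withdrawn consent, pregnancy and termination by the sponsor or regulators. The escalation component has its own stratified log-rank test and stratified Cox model (SAP 9.3). Discontinuation as primary failure enters the stratified Mantel-Haenszel test (SAP 9.2.1).
- **Stratifying would make the discontinuation and relapse tests agree.** Relapse counts only withdrawals for escalation, so the events would still differ. Relapse is analysed in the ITT set with three strata, so the population would differ too if all randomized subjects were used for discontinuation.

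One practical objection also stands. The change is not wholly free of paperwork, because SAP section 12 currently declares no departure from the protocol's analysis.

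**Conclusion.** The point holds as a minor one. The discontinuation test names no strata although the trial randomizes by them and stratifies its relapse log-rank test. The test is valid, and slightly conservative if discontinuation risk differs by pathway.

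Under a hazard ratio of 0.6 and the assumed rates and stratum sizes, the cost is about 0 points of power with no or mild pathway differences and about 1 to 2 points with moderate ones. Larger losses need extreme differences, such as placebo discontinuation from 10% to 65% across strata. There is no contradiction between protocol and SAP here. The sample size and the primary and secondary conclusions are unaffected.

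**What to change.** Before unblinding, revise the sentence in SAP section 4 along these lines: *The arms will be compared by a stratified log-rank test, using the strata that Section 9.1 defines for the [all randomized / ITT] analysis set.* Choose the set in the same edit, because section 4 names none. The all randomized set brings four strata and the ITT set three. The Kaplan-Meier curves can stay pooled by arm.

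Record the departure from Protocol 9.2 in SAP section 12. The alternative, editing Protocol 9.2 itself, would need a protocol amendment under Protocol 12.1, which a point of this size does not justify.

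The cost is one sentence, one entry in section 12 and one option in the analysis program.
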